The PI developed a web-based intervention (UV4.me) that was found to significantly decrease UV exposure and increase skin protection behaviors among young adults in a randomized controlled trial (RCT) of nearly 1000 participants recruited from a consumer research panel. The intervention (UV4.me) is individually-tailored, interactive, and multimedia in nature, and based on the Integrative Model of Behavioral Prediction. Similar to other online trials, 73% of eligible individuals completed the baseline questionnaire, 70% who were randomized to the intervention accessed it, and 68% accessed it and completed at least one module. However, we have an opportunity to increase the engagement, implementation, and ultimately, the impact of UV4.me. We will do this by adding several key interactive features/strategies suggested by participants, our data, and supported by the literature (i.e., by creating a mobile version, adding incentives embedded in the intervention, a behavior tracking and feedback feature, peer interaction component, and ongoing news updates). This Hybrid Type 2 dissemination-effectiveness project's purpose is to implement the enhanced intervention (UV4.me2) with adults aged 18-25 years at moderate to high risk of developing skin cancer and evaluate the intervention's effectiveness in a sample recruited online through national dissemination to the general population. This project will use the RE-AIM framework to determine the reach, effectiveness, implementation, maintenance, and cost of UV4.me2.

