4.0 Study Design

4.1 Recruitment

A small number of human subjects will participate in acceptability testing (20-25 participants) and usability testing (12-15 participants). After acceptability and usability testing, a national sample of 1500 human subjects will be recruited to participate in the Randomized Control Trial (RCT). Therefore, we have a lower accrual goal of 1,532 and an upper accrual goal of 1,540.

Five types of online sources will be used to reach young adults: 1) national non-profit and for-profit skincare organizations (e.g., the Melanoma Research Foundation and Blue Lizard Sunscreen), 2) Google Adwords, 3) paid Facebook ads, 4) a consumer research panel, and 5) word of mouth (e.g., unpaid study Facebook page, earned social and traditional media [free publicity from a third party]). Google Adwords and Facebook are common online recruitment sources for young adults that can produce cost-effective, representative, and quality samples/data 87-95. Facebook is the largest social networking website and the second most popular website in the US after Google 96. Because some participants may know one another (e.g., from Facebook), we will inquire about/control for contamination between intervention conditions. Consumer research panels possess the qualities of Google Adwords and Facebook and can also produce guaranteed enrollment/data collection within a specified time-frame and budget 97-103, as occurred in the original UV4.me study. The team will refine web banner ads and create a Facebook study webpage to recruit individuals from the five online sources. Enrolled participants will be informed about the Facebook page, and non-enrolled individuals will be able to find the publicly available page organically by being referred by friends or searching Facebook or the web for related topics. To facilitate recruitment via Google and Facebook (also Bing and Yahoo), we will work with young adults and www.PatientRecruitmentOnline.com to help develop our keywords, ads, and recruitment plans. PatientRecruitmentOnline.com is made up of experts in online marketing specifically for health-related study recruitment. They will assist us in refining our keywords, ads, recruitment campaign, homepage, and enrollment process.

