Randomized Controlled Trial. RCT participants will complete a baseline survey focusing on exposure and protection behaviors that takes a maximum of approximately 15 minutes on average. The study statistician will create a randomization scheme to randomize enrolled participants on a 2:2:1 basis to either the UV4.me2, UV4.me, or the e-pamphlet condition, respectively. Participants will not be informed of the differences in the intervention conditions beyond that they will all be online skin cancer risk

reduction interventions. Participants will then be asked to complete follow-up assessments at 3, 6, and 12 months post-baseline.

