Efficacy. We will compare demographics across randomization arms using chi-squares and ANOVAs for categorical and continuous data, respectively. The primary outcomes are baseline to 3-month changes in UV exposure and protection. We will use multivariable linear regression to compare the effectiveness of UV4.me2 with UV4.me, and UV4.me2 with the e-pamphlet. We will not compare UV4.me to the epamphlet because UV4.me compared to a control condition was established in the prior study. Covariates in these models will include study arm, recruitment month/season, US region, and demographic factors identified as significantly imbalanced across arms (confounders). Analyses will be performed separately for the two primary outcomes. Variance stabilizing transformations may be applied as needed. Hypothesis tests will be two-sided with a 1.25% Type I error to account for multiple testing (2 intervention comparisons x 2 outcomes). Based on our data, experience, the enhanced study procedures, and the consumer research panel's experiences with young adults, we anticipate attrition of approximately 20% at each time-point. With 1500 young adults at baseline, we anticipate collecting 3-month follow-up data from 1200 participants, with 240 from the e-pamphlet arm and 480 participants from each of the other arms. The means (SDs) of the baseline to 3-month changes in UV exposure and protection indexes from the prior study control arm were 0.34 (0.74) and -0.37 (0.90), respectively. Given these parameters, we will have 80% power to detect small standardized effect sizes of 0.22 between the UV4.me2 and UV4.me arms, and 0.26 between the UV4.me2 and the e-pamphlet. These correspond to small detectable differences between intervention arms of 0.16 and 0.19 in baseline to 3-month changes in UV exposure and protection indexes, respectively. We will be able to detect slightly larger differences when the UV4.me2 and e-pamphlet arms are compared (detectable differences - UV exposure: 0.20; protection: 0.24). Analyses will assume that missingness depends on observed data (i.e., missing at random; MAR) 141. For drop-outs, the reason for attrition will be analyzed if available to search for evidence of informative missingness. Baseline variables will be compared by whether participants drop out or not. Significant variables will be added to the model to strengthen our MAR assumption. As a sensitivity analysis, we will use a shared parameter model with the assumption of missing not at random 142. If large changes in parameter estimation are found, we will use the results from the shared parameter model.

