
13.2 Statistical Analyses for Secondary Aims

Maintenance. We will compare baseline to 6- and 12-month changes in UV exposure and protection across study arms. Tests will be two-sided with a 5% type I error for these secondary analyses. We anticipate having follow-up data from approximately 960 and 768 participants at 6- and 12-months, respectively. This will allow for 154 participants in the e-pamphlet arm and 307 in each of the other two arms at 12 months. Detectable differences with 80% power are presented in Table 3.

Implementation. Using BeHealth's Wasabi data management system, we will create a summary index representing how frequently and for how long participants are logged into the interventions and how many sections are completed and determine whether this index is associated with behavioral outcomes. Whether and when a user accesses the e-pamphlet will be noted. We have experience using Google Analytics "goals" to track how frequently individual pages within modules are accessed. We will ask participants about their satisfaction with the study/intervention and selected components (e.g., the enhanced features) both from within the interventions and a one-month follow-up inquiry. These implementation variables will also be linked to participant source (i.e., skin protection organizations, Google Adwords, Facebook ads, consumer research panel) when possible so that sources can be compared in terms of participant intervention implementation. We will use the methods described for Aim 2 to compare these utilization and satisfaction measures across study arms, and Spearman's correlation to measure the level of association between implementation metrics and longitudinal changes in UV exposure and protection indexes within and across study arms. Tests will be two-sided with a 5% type I error for these secondary analyses. We anticipate 1350 participants at 1-month follow-up (epamphlet = 270, others = 540). Whether individuals click into the pages with discounts and free samples from skincare companies will be noted. We will assess whether accessing more incentives within the interventions is associated with greater intervention utilization and better behavioral outcomes.

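### Recruitment source is recorded but not used in the effectiveness analysis, so the plan has no estimate of whether the UV4.me2 effect holds outside the consumer panel

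*Combined protocol and SAP*

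**What the plan says.** **Aim.** Section 1.0 describes the earlier study as a "randomized controlled trial (RCT) of nearly 1000 participants recruited from a consumer research panel". It says that this trial will "evaluate the intervention's effectiveness in a sample recruited online through national dissemination to the general population".

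**Recruitment.** Section 4.1 states: "Five types of online sources will be used to reach young adults". The consumer research panel is one of the five. Panels, it says, "can also produce guaranteed enrollment/data collection within a specified time-frame and budget". No quota or cap by source is stated, nor is the share of the 1500 expected from each.

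**Randomisation.** Section 4.3 states: "The study statistician will create a randomization scheme to randomize enrolled participants on a 2:2:1 basis". No stratification factor is named.

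**Recording of source.** Section 4.4.1 (Reach) tracks source by a pixel in each advertisement and by asking participants how they heard of the study.

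**Use of source.** In 13.1 (Reach), enrolment and representativeness are compared by source. In 13.2, implementation measures are linked to source where possible, "so that sources can be compared in terms of participant intervention implementation".

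**Effectiveness model.** Section 13.1 states: "Covariates in these models will include study arm, recruitment month/season, US region, and demographic factors identified as significantly imbalanced across arms". Source is absent. It could enter only through the rule that baseline variables which differ significantly between dropouts and completers are added. No arm-by-source term or by-source estimate is planned for the two primary outcomes.

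**The concern.** The trial's new claim is about people reached through dissemination, whereas the earlier evidence came from a panel. The pooled estimate averages over both groups in proportions that the plan does not fix. If the UV4.me2 effect differs between panel members and others, the pooled figure depends on the panel's share, and nothing in the effectiveness analysis would show it. The by-source reach analysis would reveal the share, but not whether the effect holds outside the panel.

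The documents give some reason to think that source could matter. Section 4.1 expects that some participants may know one another, with Facebook as the example, and raises contamination between arms; this would weaken the contrast more in some sources than in others. Section 16.0 describes entry data from the panel that are used to confirm eligibility and consistency of response, and describes no counterpart for the other sources. Neither point shows that effects differ. Together they make the question worth asking in advance rather than after the results are known.

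There are two smaller stakes. A covariate that predicts outcome improves precision. If completion differs by source, a missing-at-random model that includes source is more credible than one that leaves it to a significance screen.

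**Working it through.** **Inputs from 13.1.** Analysed numbers at 3 months: 480, 480 and 240 (UV4.me2, UV4.me, e-pamphlet). Two-sided alpha 0.05/4 = 0.0125. Power 80%. SDs 0.74 and 0.90. **Assumption.** The panel share p is not in the documents, so a range is shown. Completion is taken as equal across sources.

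**1. The plan's own figures.** Detectable d = (2.498 + 0.842) × √(1/n₁ + 1/n₂).
- UV4.me2 v UV4.me: 3.339 × √(2/480) = 0.2156, stated as 0.22.
- UV4.me2 v e-pamphlet: 3.339 × √(1/480 + 1/240) = 0.2640, stated as 0.26.
- Raw differences: 0.160 and 0.194, then 0.195 and 0.238; stated as 0.16 and 0.19, then 0.20 and 0.24.

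The plan's figures reproduce.

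**2. Does omitting source bias the comparison?** No. In 40,000 simulated two-arm trials (960 analysed, half from the panel, simple randomisation), type I error was 1.29% with a 0.5 SD difference in outcome between sources and 1.34% with none, against a nominal 1.25%. With 600 v 600 randomised, the chance imbalance in panel share has SD √(p(1−p) × 2/600): 2.9 percentage points at p = 50%, and 2.5 at 25% or 75%.

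**3. What a source covariate buys.** If source explained 5% of outcome variance (assumed), power would rise from 80.0% to 82.3% and detectable d would fall from 0.216 to 0.210. If it explained nothing, neither would change.

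**4. How large a panel-only effect would have to be.** Pooled effect = p × d(panel) + (1−p) × d(non-panel). Set d(non-panel) = 0 and the pooled effect to 0.22, so d(panel) = 0.22/p. The last column takes a panel-only effect of 0.40 SD and gives Φ(0.40p/√(2/480) − 2.498).

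| Panel share | d(panel) for pooled 0.22 | Chance that pooled UV4.me2 v UV4.me is significant, panel-only effect 0.40 |
|---|---|---|
| 25% | 0.88 | 17% |
| 50% | 0.44 | 73% |
| 75% | 0.29 | 98% |

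**5. Precision of a non-panel estimate.** SE = √[(1/n₁ + 1/n₂)/(1−p)], in SD units; the half-width of the 95% interval is 1.96 × SE.

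| Contrast | p = 50% | p = 70% |
|---|---|---|
| UV4.me2 v UV4.me | 0.091 (±0.18) | 0.118 (±0.23) |
| UV4.me2 v e-pamphlet | 0.112 (±0.22) | 0.144 (±0.28) |

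If the true non-panel effect were zero, the interval for UV4.me2 v UV4.me would exclude 0.22 with probability Φ(0.22/SE − 1.96): about 67% at p = 50% and 46% at p = 70%.

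**6. Arm-by-source difference.** SE = √[(2/480)(1/p + 1/(1−p))] = 0.129 at p = 50% and 0.149 at 25% or 75%. At two-sided 5% and 80% power, the detectable difference in effect is 2.80 × SE: 0.36 and 0.42 SD. For a panel-only effect just large enough to give the unrounded pooled 0.2156 (0.86, 0.43 and 0.29 SD at p = 25%, 50% and 75%), power is about 100%, 92% and 49%.

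**The case against.** The strongest reply is that this is a refinement and not a flaw. Randomisation protects the arm comparison, and step 2 bears that out. Neither a main-effect covariate nor stratification by source would reveal an effect confined to the panel. The harm needs both a large panel share and strong effect modification, and the documents establish neither. With five equal sources (20% each), a panel-only effect would have to be 0.22/0.20 = 1.10 SD. The panel is itself one of the planned routes of dissemination, 4.1 credits panels with the same merits as the other online sources, and Hypothesis 2 makes no claim by source. All of this stands.

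The reply on missing data stands in part. Section 13.1 already screens baseline variables against dropout and adds a missing-not-at-random sensitivity model. If 1500 participants dropped out at 15% v 25% by panel status (assumed rates), a two-sided 5% test would find it with about 99% power for panel shares of 20% to 70%. But the plan does not say whether source counts as a baseline variable for that screen. Naming it removes the doubt.

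A reader might also infer that panel members answer differently because they are practised, paid respondents. The documents do not say so, and 4.5 pays participants in every arm for completing assessments. Nor would a panel result merely repeat the earlier trial: both primary contrasts involve UV4.me2, which is new.

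What the reply does not meet is that a trial meant to carry a panel result to a wider public records source and plans no effect estimate by it.

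**Conclusion.** This is a cheap improvement. The omission from the model list, and the absence of any by-source behavioural estimate, are plain in 13.1. The consequence is for generalisability, with a modest gain available in precision and in support for the missing-at-random assumption. Sample size, alpha and the validity of the randomised comparison are unaffected.

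The size depends on a panel share that the documents do not give. At 25%, a panel-only explanation of a pooled 0.22 needs an implausible 0.88 SD. At 50% it needs 0.44 and at 75% only 0.29. The point is material mainly if the panel supplies about half or more of the sample.

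Two stronger readings should be resisted. A reader might infer that the trial is set to report a panel-driven result as a general-population one; the documents give neither the share nor any sign of a source-specific effect. A reader might also infer that source is excluded from the randomisation; 4.3 simply does not describe the scheme beyond 2:2:1. The remedy has limits too. At a 70% share, an interval of ±0.23 around zero still includes 0.22, so the non-panel estimate would inform the general-population conclusion without necessarily settling it.

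**What to change.** In 13.1 (Efficacy):

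1. Name recruitment source, with a category for unknown, as a fixed covariate in both primary models, rather than leaving it to the dropout screen.
2. Pre-specify, as supportive estimates, UV4.me2 v UV4.me and UV4.me2 v e-pamphlet for each primary outcome, in panel and in non-panel participants, with 95% confidence intervals. Add the panel/non-panel difference in each effect with its interval, and report the panel share beside them. State in advance on which side participants of unknown source are counted.
3. Interpret these as estimates. Do not add a rule that the non-panel estimate need only agree in direction with the pooled one: if the true non-panel effect were zero, it would be met at least half the time.

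Stratifying the randomisation by panel status is optional; it would not by itself answer the question. The primary tests and the 1.25% level are unchanged.

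The cost is one covariate already collected and one extra table. The drawback is limited precision outside the panel, most of all if the panel dominates.

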4.4 Measures

4.4.1 Measures for Primary Aims

Screener. Participants will be screened with [name] 9-item Brief Skin Cancer Risk Assessment Tool (see Inclusion Criteria above) 104. Internal and test-retest reliability compare favorably to those reported in the literature for similar items/scales 104. Participants will be required to understand English and have access to the internet via any modality (e.g., computer, smartphone) at least weekly.

Demographics. Standard demographic items used by the census will assess: sex, age/birthdate, race/ethnicity, region of residence, education, income, and employment. We will include items on web use from the Health Information National Trends Survey 121, and will inquire about family history of skin cancer.

Social Desirability. Social Desirability will be assessed using the 4-item Brief Social Desirability Scale that has demonstrated adequate internal reliability and validity among young adults 122.

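### Apart from US region, demographics reach the primary efficacy models only through significance tests on the trial's own data; a fixed covariate list would be better and costs almost nothing

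*Combined protocol and SAP*

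**What the plan says.** The Efficacy paragraph of section 13.1 sets out the covariate rule in three steps.

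- It starts with tests of balance: "We will compare demographics across randomization arms using chi-squares and ANOVAs for categorical and continuous data, respectively".
- It then defines the model. Arm, month/season and region are unconditional. To these it adds "demographic factors identified as significantly imbalanced across arms (confounders"), so the other demographics depend on the test.
- Under missing data it opens a second route: "Baseline variables will be compared by whether participants drop out or not", followed by "Significant variables will be added to the model to strengthen our MAR assumption".

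Neither test has a stated significance level. The paragraph does not say whether balance is tested in the 1,500 randomised or in the 1,200 expected at 3 months.

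Section 4.4.1 lists the demographics as "sex, age/birthdate, race/ethnicity, region of residence, education, income, and employment". Region is one of these seven, so six are left to the tests. The same paragraph of 4.4.1 also covers web use and family history of skin cancer, and 13.1 does not say whether these count as demographics to be tested.

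**The concern.** Section 4.3 describes a 2:2:1 randomisation and states no stratification factor. Data-quality problems aside, a significant baseline difference between randomised arms is a chance event. It says nothing about whether the factor predicts change in UV exposure or protection, which is what makes a covariate worth having. A prognostic factor that happens to be balanced stays out, and a factor of no prognostic value that happens to be imbalanced goes in. Calling the selected factors confounders does not alter this.

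Two things are at stake. The first is precision that variables already in hand could supply. The second is prespecification: the adjustment set for all four primary tests is unknown until the data have been examined. Because the thresholds, the tested population and the tested variables are left open, two analysts could reach different primary models from the same data. Section 13.2 reuses these methods to compare utilization and satisfaction across arms, so the rule carries over there.

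**Working it through.** **Inputs from section 13.1.** 480, 480 and 240 participants analysed at 3 months; two-sided alpha 0.05/4 = 0.0125; 80% power; SDs of change 0.74 (exposure) and 0.90 (protection).

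**Assumed, not in the documents.** A 5% level for the balance tests; six independent demographics; R², the share of the variance of change that they explain.

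**1. The plan's own figures.** Detectable d = (z for 1 - 0.0125/2, plus z for 0.80) × √(1/n1 + 1/n2).

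- UV4.me2 vs UV4.me: (2.498 + 0.842) × √(1/480 + 1/480) = 0.2156 (stated 0.22).
- UV4.me2 vs e-pamphlet: (2.498 + 0.842) × √(1/480 + 1/240) = 0.2640 (stated 0.26).
- Multiplied by the SDs: 0.1595 and 0.1940 for the first comparison, 0.1954 and 0.2376 for the second (stated 0.16, 0.19, 0.20, 0.24).

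All of them reproduce. They use unadjusted SDs and claim no gain from covariates.

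**2. How often the imbalance rule selects anything.** Expected number flagged = 6 × 0.05 = 0.30. P(none) = 0.95^6 = 73.5%. P(at least one) = 26.5%.

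**3. Precision recovered.** Simulation with 600/600/300 randomised, about 20% dropout, least squares and 3,000 runs per R². The mean standard error (SE) is for UV4.me2 vs UV4.me in SD units. The dropout column assumes that two of the six demographics predict dropout (log odds ratio 0.25 per SD).

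| R² | No demographics | Imbalance rule | Rule plus dropout route | All six |
|---|---|---|---|---|
| 0.05 | 0.0644 | 0.0643 | 0.0638 | 0.0629 |
| 0.10 | 0.0644 | 0.0643 | 0.0632 | 0.0613 |
| 0.20 | 0.0644 | 0.0641 | 0.0619 | 0.0577 |

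Share of the gain captured by the imbalance rule alone:

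- R² 0.05: 0.0001/0.0015 = 7%
- R² 0.10: 0.0001/0.0031 = 3%
- R² 0.20: 0.0003/0.0067 = 4%

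With the dropout route added, the shares are 0.0006/0.0015, 0.0012/0.0031 and 0.0025/0.0067, or about 37-40%. In that scenario 2.3 of the six entered on average.

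**4. Power with fixed adjustment.** The residual SD becomes SD × √(1 - R²).

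| R² | Power at 0.22 (480 vs 480) | Power at 0.26 (480 vs 240) |
|---|---|---|
| 0 | 81.9% | 78.6% |
| 0.02 | 82.8% | 79.5% |
| 0.05 | 84.1% | 81.0% |
| 0.10 | 86.3% | 83.4% |
| 0.20 | 90.5% | 88.1% |

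The gains are about 1, 2, 4-5 and 9 points. The 78.6% in the first row is a rounding effect: the 80% point is 0.264, not 0.26. Under the imbalance rule alone, power at 0.22 stays between 81.9% and 82.3% for R² up to 0.20.

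**5. Type I error.** With 20,000 null runs at 480/480/240 and nominal 1.25%, the rule gave 1.37% against 1.40% with all six covariates at R² = 0.10, and 1.09% against 1.20% at R² = 0.30. The Monte Carlo standard error is about 0.08 points. There is no sign that the rule inflates the error rate.

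**The case against.** The strongest defence is that the plan is valid and meets its own target. The power statement asks nothing of the covariates, so nothing promised is lost. Season and region, both plausible drivers of UV behaviour, are always in the model. The outcome is a change score, so stable differences in behaviour between demographic groups cancel; only prediction of change helps, and the documents give no evidence that sex or any other demographic predicts it. The larger gains rest on R² values of 10-20% that nobody has shown. At 2% the gain is about one point. The simulation treated the six factors as independent, although education, income and employment probably are not, and it left out season and region. It also did not model the exact list proposed below.

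All of this stands, and it limits the size of the point. It does not defend choosing covariates by chance imbalance.

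Three stronger readings are tempting but not supported:

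- *Demographics enter only if imbalanced.* Region is always in, and section 13.1 also admits baseline variables related to dropout.
- *The plan as a whole recovers almost no precision.* That describes the imbalance rule taken alone. The dropout route recovered about 40% in one assumed scenario, and the true share depends on which variables predict dropout.
- *The trial is underpowered or its tests are distorted.* The detectable effects reproduce without any covariate gain. The type I differences between the rule and fixed adjustment are within or near simulation noise, so no argument should rest on the tests being conservative either.

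**Conclusion.** The point holds as a nearly free improvement, not as an error that threatens validity. Apart from region, the demographics in the primary models are settled by data-driven tests with no stated threshold. The arm-imbalance test selects on chance. The dropout test has a separate rationale in the missing-at-random assumption, but it is likewise settled only after the data are seen. The cost is forgone precision and a primary model that is not fixed in advance.

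The 73% figure rests on six independent tests at 5%. The gain of 1 to 9 power points rests on an R² between 2% and 20% that the documents do not give, and it is illustrative for any particular list. The case for prespecification depends on none of these assumptions.

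**What to change.** In the Efficacy paragraph of section 13.1, replace the clause on significantly imbalanced demographics with a fixed list of baseline covariates that enters every efficacy model whatever the observed balance. One workable list is sex, age, race/ethnicity, education and the screening risk score from section 4.2, next to recruitment month/season and region. State how each is coded.

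Keep the baseline comparison between arms as a descriptive table, without significance tests that feed the model. Leave the dropout step in place for its missing-at-random purpose; it would then only add variables that are not already on the list.

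The cost is a sentence or two in the plan and a few degrees of freedom out of about 1,200. No new data are needed.

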2.3 Hypotheses

Hypothesis 1. We hypothesize that the study enrollment rate will be greater than in the original UV4.me efficacy study and that our sample will be representative of national demographics of young adults other than race/ethnicity (associated with skin cancer risk), indicating potential generalizability.

Hypothesis 2. We hypothesize that the UV4.me2 will be the most effective intervention, followed by UV4.me.

Hypothesis 3. We hypothesize that maintenance outcomes will be best in the UV4.me2 group, next best for UV4.me, and least for the e-pamphlet group.

Hypothesis 4. We hypothesize that greater intervention utilization (e.g., logins, module completion) and satisfaction will be associated with better behavioral outcomes

Hypothesis 5. We hypothesize that UV4.me2 and UV4.me will have higher incremental costs than the epamphlet. However, because UV4.me2 and UV4.me are also expected to result in better behavioral outcomes, we will assess cost-effectiveness to address whether these interventions are worth the additional costs.

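### Optional gain, not an error: testing the four primary efficacy comparisons by Holm step-down instead of a fixed 1.25% keeps the 5% bound and can only add power at the same N

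*Combined protocol and SAP*

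**What the plan says.** Section 13.1 (Efficacy) names two primary outcomes: "The primary outcomes are baseline to 3-month changes in UV exposure and protection". It names two comparisons, to "compare the effectiveness of UV4.me2 with UV4.me, and UV4.me2 with the e-pamphlet", both of which use the UV4.me2 arm. On structure it says: "Analyses will be performed separately for the two primary outcomes". On error control: "Hypothesis tests will be two-sided with a 1.25% Type I error to account for multiple testing (2 intervention comparisons x 2 outcomes").

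The sample-size statement is built on that level: "we will have 80% power to detect small standardized effect sizes of 0.22 between the UV4.me2 and UV4.me arms", and 0.26 against the e-pamphlet. Section 4.3 will "randomize enrolled participants on a 2:2:1 basis", and section 13.1 expects 480, 480 and 240 participants with 3-month data.

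Section 2.3, Hypothesis 2, reads: "We hypothesize that the UV4.me2 will be the most effective intervention, followed by UV4.me". It ranks the arms. It does not say that the effect will appear on both outcomes.

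On missing data, section 13.1 adds: "If large changes in parameter estimation are found, we will use the results from the shared parameter model".

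No step-down, hierarchical or gatekeeping rule appears anywhere in the documents.

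**The concern.** The fixed rule holds every test at one quarter of 5%, even after other tests have been rejected. Once a hypothesis has been rejected, fewer remain to be protected, and a step-down procedure can relax the level for those. Because the outcomes are analysed separately, each of the four tests supports its own conclusion about UV4.me2. What is at stake is the chance of missing a real effect on one outcome or against one comparator when others have been shown. The validity of the plan is not in question.

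**Working it through.** **Inputs.** From section 13.1: four tests, two-sided 0.0125 each, 480/480/240 completers, SDs of change 0.74 (exposure) and 0.90 (protection), power 80%. Not in the documents, so assumed: the correlation between outcomes on the benefit scale, taken as 0 to 0.5, with -0.5 to 0.95 as a stress range.

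**1. The plan's error rate.** 4 x 0.0125 = 0.05. If the tests were independent, 1 - (1 - 0.0125)^4 = 4.91%. The split is valid.

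**2. The plan's power.** Detectable effect = (z for two-sided 0.0125 + z for 80% power) x SE, with 2.4977 + 0.8416 = 3.3393.
- UV4.me2 vs UV4.me: SE = sqrt(1/480 + 1/480) = 0.06455, giving 0.2156 (stated 0.22).
- UV4.me2 vs e-pamphlet: SE = sqrt(1/480 + 1/240) = 0.07906, giving 0.2640 (stated 0.26).
- Multiplied by the SDs: 0.160 and 0.194, then 0.195 and 0.238 (stated 0.16, 0.19, 0.20, 0.24).

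The plan's figures reproduce. At the rounded effects themselves, power is 81.9% for 0.22 and 78.6% for 0.26.

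**3. Why Holm cannot lose.** The ordered p-values are compared with 0.05/4 = 0.0125, 0.05/3 = 0.0167, 0.05/2 = 0.025 and 0.05, stopping at the first failure. Every threshold is at least 0.0125, so every p-value that passes the fixed rule passes here. The first true null to be reached faces at most 0.05 divided by the number of true nulls, so the family-wise error is at most 5% under any dependence. The first threshold is the same in both rules, so the chance of at least one rejection does not change.

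**4. Size of the gain.** Four jointly normal test statistics were simulated, with 400,000 to 1,000,000 draws per scenario. The two comparisons within an outcome share an arm, so they correlate (1/480) / sqrt((2/480) x (3/480)) = 1/sqrt(6) = 0.408. Each real effect is set at exactly 80% power under the fixed rule, with outcome correlation 0 to 0.5.

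| Real effects | Per-test power, fixed to Holm | Actual family-wise error, fixed to Holm |
|---|---|---|
| Four | 80% to 88-89% | no true null |
| Three | 80% to about 85% | 1.25% to 3.8-3.9% |
| Two | 80% to 82% | 2.3-2.5% to 4.0-4.3% |
| One | 80% to 80% | 3.5-3.7% to 4.3-4.6% |
| None | not applicable | 4.5-4.8%, unchanged |

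With four real effects, the chance of rejecting all four rises from 46-52% to 71-74%. With three very large effects and one true null, the actual family-wise error goes from 1.25% to 5%, its limit. No draw was rejected by the fixed rule but not by Holm.

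**5. Sensitivity.** With four real effects at 80%, Holm gives about 90% at outcome correlation -0.5, 87.2% at 0.8 and 86.4% at 0.95. The ceiling for a test at exactly 80% is its power at level 0.05: Phi(3.3393 - 1.9600) = 91.6%, a gain of 11.6 points. A test with less power can gain up to about 21 points.

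The contrasts need not gain equally. Planned sizes on both contrasts imply that UV4.me beats the e-pamphlet by only 0.2640 - 0.2156 = 0.048 SD. With larger assumed UV4.me effects against the e-pamphlet (both outcomes alike, correlation 0):
- UV4.me effect 0.20, UV4.me2 vs UV4.me at 0.216: UV4.me contrast 80% to 91%, e-pamphlet contrast 99.7% to 99.9%.
- UV4.me effect 0.10, UV4.me2 vs e-pamphlet at 0.264: 52% to 65%, and 80% to 86%.
- UV4.me effect 0.20, UV4.me2 vs e-pamphlet at 0.264: 7% to 11%, and 80% to 82.5%.

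**The case against.** The strongest reply is that there is no defect. The plan names its four tests, splits alpha correctly and reaches the power it states. The fixed rule also has real merits. Each test stands alone, and its 98.75% confidence interval always agrees with its test. Under Holm, at planned sizes, at least one contrast is rejected while its 98.75% interval includes zero in about 27-30% of trials if all four effects are real, and in about 1% if one is. The outcomes also become linked. If all four effects are real and a change of model made both p-values of one outcome clearly non-significant, the other outcome's conclusions would change in about 11-13% of trials. Under the fixed rule that never happens. All of this stands, and it is why the change is optional.

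It is also fair to say that four real effects at planned sizes fits the trial's premise poorly. Section 13.1 treats the benefit of UV4.me over a control condition as already established, yet that scenario leaves UV4.me only 0.048 SD ahead of the e-pamphlet. This does not count against Holm, which gains more on some contrasts when the effects are unequal. It does mean that the 88-89% figure is not a forecast for this trial.

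A reader might infer that the plan mishandles alpha or is underpowered, or that Holm would bring a gain of up to 9 points on every test. The documents support neither. The plan's own figures reproduce. The size of the gain depends on how many effects are real, how large they are and how the outcomes correlate; the documents do not settle the first or give the last. Hypothesis 2 ranks the arms without promising an effect on both outcomes.

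**Conclusion.** The concern holds as a cheap improvement to a valid plan. That Holm stays within 5% and never loses a fixed-rule rejection is a mathematical result and needs no assumption about correlation. The size does rest on assumptions: each real effect has exactly 80% power under the fixed rule, and the outcome correlation on the benefit scale is 0 to 0.5. Outside those conditions the gain may be smaller or larger and may differ by contrast. Nine points is not a bound.

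Two limits apply. The 5% covers the four efficacy tests only; the Reach tests under Primary Aim 1 carry their own 5% levels. Holm also does not cure the data-dependent model choices in section 13.1, namely covariates chosen by significance and the switch to the shared parameter model triggered by the estimates. The fixed rule does not cure them either.

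**What to change.** Before any by-arm outcome analysis, replace the multiplicity sentence in section 13.1 with:

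*The four primary efficacy p-values (2 comparisons x 2 outcomes) will be tested together by the Holm step-down procedure at a family-wise two-sided 5% level, using p-values from the final primary model for each outcome.*

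Keep 0.22 and 0.26 as conservative planning figures. Report 98.75% confidence intervals for all four contrasts, with a note that an interval may include zero where Holm rejects.

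The cost is one replaced sentence and one reporting note, with no change to N. The sponsor accepts in return the interval mismatch, the linked outcomes and a higher actual family-wise error within the 5% bound. If these are judged not worth the gain, the existing sentence can stand.
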